9.2 Arm 2: FOLFIRB

| REQUIRED STUDIES   | PRE
STUDY | $\Sigma$ |         |         |         |         |         |         |         |         |          | $\Omega$
Follow up
prior to
prog | % |   |   |
|--|--------------|----------|---------|---------|---------|---------|---------|---------|---------|---------|----------|---|---|---|---|
|  |              | Cycle 1  |         | Cycle 2 |         | Cycle 3 |         | Cycle 4 |         | Cycle 5 |          |   |   |   |   |
|  |              | Wk
1  | Wk
2 | Wk
3 | Wk
4 | Wk
5 | Wk
6 | Wk
7 | Wk
8 | Wk
9 | Wk
10 |   |   |   |   |
| PHYSICAL  |              |          |         |         |         |         |         |         |         |         |          |   |   |   |   |
| History and Physical Exam                                    | X            | X        |         | X       |         | X       |         | X       |         | X       |          | X   |   | X | X |
| Weight and Performance Status                                | X            | X        |         | X       |         | X       |         | X       |         | X       |          | X   |   |   |   |
| Disease Assessment   | X            |          |         |         |         |         |         |         |         | X       |          |   |   |   |   |
| Toxicity Notation  | X            | X        |         | X       |         | X       |         | X       |         | X       |          | X   |   | X |   |
| Baseline Abnormalities                                       | X            |          |         |         |         |         |         |         |         |         |          |   |   |   |   |
| LABORATORY tr d                            |              |          |         |         |         |         |         |         |         |         |          |   |   |   |   |
| CBC/Differential/Platelets                                   | X            | X        |         | X       |         | X       |         | X       |         | X       |          | X   |   |   |   |
| CA19-9/CEA \$  | X            | X        |         |         |         | X       |         |         |         | X       |          |   |   |   |   |
| AST/ALT, total bilirubin, serum albumin,
serum creatinine | X            | X        |         | X       |         | X       |         | X       |         | X       |          | X   |   |   |   |
| Chemistry **   | X            | X        |         | X       |         | X       |         | X       |         | X       |          | X   |   |   |   |
| X-RAYS AND SCANS c                         |              |          |         |         |         |         |         |         |         |         |          |   |   |   |   |
| CT/MRI for disease assessment                                | X            |          |         |         |         |         |         |         |         | X       |          |   |   | X |   |
| SPECIMEN SUBMISSION                                   |              |          |         |         |         |         |         |         |         |         |          |   |   |   |   |
| Tissue block or slides for TM (required) $\delta$            | X            |          |         |         |         |         |         |         |         |         |          |   |   |   |   |
| Archival tissue slides for TM (required) $\delta$            | X            |          |         |         |         |         |         |         |         |         |          |   |   |   |   |
| Blood for TM (required) $\delta$                             | X            |          |         |         |         |         |         |         |         |         |          |   |   |   |   |
| Tissue for banking (optional) $\delta$                       | X            |          |         |         |         |         |         |         |         |         |          |   |   |   |   |
| TREATMENT   |              |          |         |         |         |         |         |         |         |         |          |   |   |   |   |
| Irinotecan $\beta$   |              | X        |         | X       |         | X       |         | X       |         | X       |          | X   |   |   |   |
| Leucovorin $\beta$   |              | X        |         | X       |         | X       |         | X       |         | X       |          | X   |   |   |   |
| Fluorouracil bolus $\alpha$                                  |              | X        |         | X       |         | X       |         | X       |         | X       |          | X   |   |   |   |
| Fluorouracil $\gamma$  |              | X        |         | X       |         | X       |         | X       |         | X       |          | X   |   |   |   |

Click here for [footnotes](#).

**Footnotes:**

- ∑ Protocol treatment and physical, laboratory, and scan parameters will continue at these intervals indicated in the Cycle 2-5 columns until progression of disease or until patient has met any of the guidelines in [Section 7.6](#).
- Ω After off treatment prior to disease progression, scans for disease assessment and physical assessments (with lab tests performed at the discretion of the treating investigator) should take place every 8 weeks until progression.
- % After off treatment following disease progression, physical assessments (with lab tests performed at the discretion of the treating investigator) should take place once every 3 months for three years from the time of registration.
- ι Oral capsule taken twice daily on Days 1-7 of every cycle. Day 3 dose should be taken at treating institution 1 hour ( $\pm$  30 minutes) prior to irinotecan (see [Section 7.2](#)).
- ϕ Infusion to be given on Day 3 of every cycle (see [Section 7.2](#)).
- £ Infusion to be given starting on Day 3 over 46-48 hours (see [Section 7.2](#)).
- α Bolus to be given on Day 1 prior to 46 hour infusion (see [Section 7.3](#)).
- β Infusion to be given on Day 1 of every cycle (see [Section 7.3](#)).
- γ Infusion to be given starting on Day 1 over 46-48 hours (see [Section 7.3](#)).
- δ See [Section 15.0](#) for more information.
- \*\* BUN, alkaline phosphatase, sodium, potassium, calcium, glucose, albumin, chloride, carbon dioxide/bicarbonate
- π Labs do not need to be repeated if pre-study labs were done within 7 days prior to Cycle 1 Day 1.
- \$ CA19-9 should be repeated every 4 weeks if abnormal at baseline. If CA19-9 normal at baseline, CEA must be tested and if CEA is abnormal, should be repeated every 4 weeks.
- △ Women of childbearing potential must have a negative serum or urine pregnancy test at screening within 28 days prior to registration. If randomized to Arm 1, serum or urine pregnancy tests are required within 72 hours prior to the first dose of study treatment. At discontinuation, a pregnancy test must be done within 4 weeks after the last dose of study drug. A pregnancy test should be done at any time there are clinical concerns for possible pregnancy.
- ◇ History prior to each treatment initiation to include a menstrual, sexual, and contraceptive use history, including date of last menstrual period (for women of childbearing potential) which will help determine the need for pregnancy testing. Similar questions regarding contraceptive use to be asked to men who are sexually active with women of childbearing potential.
- c CT or MRI, of chest, abdomen, and pelvis for disease assessment must be performed every 8 weeks while on study treatment.
- d Labs are to be drawn on Day 1 of each cycle. If the labs are satisfactory, they do not need to be repeated on Day 3 prior to FOLFIRI. If the labs drawn on Day 1 are not satisfactory for FOLFIRI therapy, the local investigator may repeat them prior to Day 3, as clinically indicated.

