- n. Patients of childbearing potential must have a negative pregnancy test within 28 days prior to registration and must not be nursing due to the risk of fetal or nursing infant harm. Women/men of reproductive potential must have agreed to use an effective contraceptive method during the study and for 6 months following completion of treatment. A woman is considered to be of "reproductive potential" if she has had menses at any time in the preceding 12 consecutive months. In addition to routine contraceptive methods, "effective contraception" also includes heterosexual celibacy and surgery intended to prevent pregnancy (or with a side-effect of pregnancy prevention) defined as a hysterectomy, bilateral oophorectomy or bilateral tubal ligation. However, if at any point a previously celibate patient chooses to become heterosexually active during the time period for use of contraceptive measures outlined in the protocol, he/she is responsible for beginning contraceptive measures.

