8.4 Dose Modification for FOLFIRI

a. Guidelines

Dose modifications for the current cycle and reduction for subsequent cycles should be carried out as shown below. Dose adjustments of irinotecan and fluorouracil infusion may be made independently based on the specific types of toxicities observed as discussed in [Sections 8.4c-i](#). For the purposes of this study, only three dose reductions of FOLFIRI are allowed. If a dose reduction is required beyond dose level -3 for irinotecan, discontinue irinotecan, but continue ABT-888, fluorouracil, and leucovorin. If a dose reduction is required beyond dose level -3 for continuous infusion fluorouracil, discontinue all protocol therapy.

**Patients should not receive ABT-888 while fluorouracil infusion and irinotecan are suspended. Skipped doses of ABT-888 during Days 3-7 of each cycle are not made up.**

Note: The fluorouracil bolus can only be skipped or discontinued.

b. Dose Levels for Treatment Modifications

| Agent                 | Starting Dose           | Level -1                    | Level -2               | Level -3               |
|-----------------------|-------------------------|-----------------------------|------------------------|------------------------|
| Fluorouracil (bolus)* | 400 mg/m    | Discontinue                 | N/A                    | N/A                    |
| Fluorouracil          | 2,400 mg/m  | 1920 mg/m       | 1600 mg/m  | 1360 mg/m  |
| Irinotecan            | 180 mg/m    | 150 mg/m        | 120 mg/m   | 100 mg/m   |
| Leucovorin**          | 400 mg/m    | No dose adjustments allowed |                        |                        |

\* Fluorouracil bolus is only given in Arm 2.

\*\* Leucovorin is always administered at 400 mg/m^2 IV prior to fluorouracil. If fluorouracil 46-48 hour infusion needs to be skipped, leucovorin must also be skipped.

α Patients known to be homozygous for UGT1A1\*28 are recommended to start irinotecan with a 30% dose reduction.

c. Neutrophil Count Decreased

Toxicity Grade Modification:

---

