#### 13.0 REGISTRATION GUIDELINES

##### 13.1 Registration Timing

Patients must be registered prior to initiation of treatment (no more than five working days prior to planned start of treatment).

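### Both arms receive two Pregnancy Category D drugs, but only Arm 1 must repeat the pregnancy test before the first dose

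*Combined protocol and SAP*

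**What the plan says.** Entry testing applies to everyone. Section 5.3n states: "Patients of childbearing potential must have a negative pregnancy test within 28 days prior to registration". It gives fetal harm as a reason and names no arm. Section 13.1 then limits the time from registration to treatment: "Patients must be registered prior to initiation of treatment (no more than five working days prior to planned start of treatment".

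The retest applies to one arm. The pregnancy-test footnote to the Study Calendar repeats the 28-day screening rule and continues: "If randomized to Arm 1, serum or urine pregnancy tests are required within 72 hours prior to the first dose of study treatment".

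The drugs concerned are shared. Sections 3.2c and 3.3c label fluorouracil and irinotecan Pregnancy Category D, and Sections 7.2 and 7.3 give both in both arms. In Arm 1 they start on Day 3 of the cycle, after ABT-888 has begun on Day 1. In Arm 2 they start on Day 1.

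Other safeguards also reach Arm 2. Section 5.3n says: "Women/men of reproductive potential must have agreed to use an effective contraceptive method during the study and for 6 months following completion of treatment". The same calendar footnote adds, without naming an arm: "A pregnancy test should be done at any time there are clinical concerns for possible pregnancy". A separate footnote asks for "History prior to each treatment initiation to include a menstrual, sexual, and contraceptive use history", to help decide whether a pregnancy test is needed.

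**The concern.** The plan treats pregnancy as unacceptable in both arms: a negative test is an entry condition, and pregnancy is a criterion for removal from protocol treatment (Section 7.6e). It then makes the check just before exposure mandatory in only one arm, although two drugs with the same pregnancy label are given in both.

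What is at stake is fetal safety. A pregnancy that begins or becomes detectable after screening must be tested for before the first dose in Arm 1. In Arm 2 it is tested for only if the history or a clinical concern prompts it, so an early pregnancy that raises no suspicion could be exposed to both drugs.

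**Working it through.** The plan states no figure for the age of the test at first dose, so there is none to reproduce. The check is date arithmetic.

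**Inputs**
- Screening test: up to 28 days before registration (Section 5.3n and the calendar footnote).
- Registration to planned start: up to five working days (Section 13.1), which is 7 calendar days with one weekend and no holiday.
- If Day 28 falls on a weekend or holiday, the limit moves to the next working day (Section 5.0).
- Arm 1 retest: within 72 hours before the first dose of study treatment, which is ABT-888 on Day 1.
- Start of irinotecan and fluorouracil: Day 3 in Arm 1 (Section 7.2), Day 1 in Arm 2 (Section 7.3).

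**Oldest mandatory test permitted in Arm 2**
- Base case: 28 + 7 = 35 days.
- With the weekend extension: a test on a Saturday, registration on the Monday 30 days later, start on the next Monday. 30 + 7 = 37 days.
- With US federal holidays, a calendar assumed here and not given in the protocol, listing every test date from September 2016 to December 2018 gives up to 39 days.

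**Oldest mandatory test permitted in Arm 1**
- At the first ABT-888 dose: 72 / 24 = 3 days.
- At the first irinotecan and fluorouracil dose: 3 + 2 = 5 days.

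**Like-for-like gap for the two shared drugs**
- Base case: 35 - 5 = 30 days.
- With the weekend extension: 37 - 5 = 32 days.

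**How many women**
The planned enrollment table in Section 2.0 has 72 + 4 = 76 women among 143 patients. Half of these is 38 in Arm 2. That is a ceiling, because it includes women with no menses in the preceding 12 months, whom Section 5.3n does not count as being of reproductive potential. The protocol does not give the number of childbearing potential.

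**The case against.** The strongest reply is that the restriction is a deliberate, graded precaution. ABT-888 is the only investigational agent. Section 3.1c reports dose-dependent embryofetal toxicity in rats and rabbits and no human pregnancy data. Arm 2 receives only commercial drugs, for which the protocol refers to the package inserts. The retest is also timed to the first ABT-888 dose, which fits that purpose. Nothing in the documents sets a retest interval for Category D drugs or says that the screening window is too wide for them.

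Much of this stands. The rule is a design choice, and the 72-hour benchmark is simply the plan's own Arm 1 rule. The ABT-888 data explain why Arm 1 is retested. They do not explain why Arm 2, which receives the same two Category D drugs, is not, and the documents give no reason.

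Four stronger readings are tempting, and the documents support none of them:
- *Arm 2 is unprotected.* It is not: entry testing, contraception and testing on clinical concern all apply. The menstrual-history footnote may apply too; its marker appears on the Arm 1 history row and not on the Arm 2 row, but it could have been lost when the table was read. These safeguards rest on adherence, self-report or suspicion, so they mitigate the gap without closing it.
- *The Arm 2 calendar omits the test.* Section 9.2 shows no pregnancy-test row, but the table has shifted columns and its content is uncertain. The point rests on the footnote sentence alone.
- *Arm 2 needs the test more, because it gets more fluorouracil.* Section 8.4 does say "Fluorouracil bolus is only given in Arm 2", but nothing in the documents links pregnancy risk to that dose difference.
- *The gap is 35 - 3 = 32 days.* That subtraction compares the first ABT-888 dose in Arm 1 with the first chemotherapy dose in Arm 2. On the base case the like-for-like figure is 30.

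**Conclusion.** The point holds as a minor safety improvement to the plan's rule. For irinotecan and fluorouracil, the last mandatory negative test can be about 35 days old in Arm 2 (about 37 with the weekend extension) against about 5 days in Arm 1, a gap of about 30 days.

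These are limits of what the plan permits: the test is done at the edge of its window and treatment starts on the fifth working day. Most women would have a more recent test. Conversely, Section 13.1 limits the planned start, so an unplanned delay could lengthen the interval.

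The number of women affected is unknown and likely to be small. No analysed endpoint changes. The Revision #1 memorandum says that accrual is permanently closed and all patients are off treatment, so the point bears on the rule, and on any later protocol that reuses this calendar, and not on current patients. A reader should not infer that anyone was harmed or that the results are affected; the documents show neither.

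**What to change.** In the pregnancy-test footnote, delete the opening condition that restricts the 72-hour sentence to Arm 1, so that it applies to women of childbearing potential in both arms. Show the test in the Arm 2 calendar (Section 9.2) with the pre-study and Cycle 1 entries only; this point gives no reason to copy the follow-up entry from the Arm 1 row. The oldest permitted mandatory test at first dose in Arm 2 would fall from about 35 days to 3.

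The cost is a footnote edit, one calendar row, and one extra urine or serum test for each Arm 2 woman of childbearing potential. The test will not always coincide with a scheduled blood draw, because another calendar footnote says: "Labs do not need to be repeated if pre-study labs were done within 7 days prior to Cycle 1 Day 1".

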## 10.0 CRITERIA FOR EVALUATION AND ENDPOINT ANALYSIS

This study will use the RECIST 1.1 guidelines. (112)

### 10.1 Measurability of Lesions

#### a. **Measurable disease**

Measurable disease is defined differently for lymph nodes compared with other disease and will be addressed in a separate section below.

1. Lesions that can be accurately measured in at least one dimension (longest diameter to be recorded) as  $\geq 2.0$  cm by chest x-ray, by  $\geq 1.0$  cm with CT or MRI scans, or  $\geq 1.0$  cm with calipers by clinical exam. All tumor measurements must be recorded in decimal fractions of centimeters (or millimeters).

The defined measurability of lesions on CT scan is based on the assumption that CT slice thickness is 0.5 cm or less. If CT scans have slice thickness greater than 0.5 cm, the minimum size for a measurable lesion should be twice the slice thickness.

2. **Malignant lymph nodes** are to be considered pathologically enlarged and measurable if it measures  $\geq 1.5$  cm in **SHORT AXIS** (greatest diameter perpendicular to the long axis of the lymph node) when assessed by scan (CT scan slice recommended being no greater than 0.5 cm).

- b. **Non-measurable disease**: All other lesions (or sites of disease), including small lesions (longest diameter  $< 1.0$  cm or pathologic lymph nodes with  $\geq 1.0$  cm to  $< 1.5$  cm short axis), are considered non-measurable disease. Bone lesions, leptomeningeal disease, ascites, pleural/pericardial effusions, lymphangitis cutis/pulmonitis, inflammatory breast disease, and abdominal masses (not followed by CT or MRI), are considered non-measurable as are previously radiated lesions that have not progressed.

#### c. **Notes on measurability**

1. For CT and MRIs, the same type of scanner should be used and the image acquisition protocol should be followed as closely as possible to prior scans. Body scans should be performed with breath-hold scanning techniques, if possible.
2. PET-CT: At present, the low dose or attenuation correction CT portion of a PET-CT is not always of optimal diagnostic CT quality for use with RECIST measurements. However, if the site can document that the CT performed as part of a PET-CT is of identical diagnostic quality to a diagnostic CT, then the CT portion of the PET-CT can be used for RECIST measurements and can be used interchangeably with conventional CT.
3. Ultrasound: Ultrasound is not useful in assessment of lesion size and should not be used as a method of measurement.
4. Cystic lesions that meet the criteria for radiographically defined simple cysts should not be considered as malignant lesions (neither measurable nor non-measurable) since they are, by definition, simple cysts.

5. If a target lesion becomes very small some radiologists indicate that it is too small to measure. If the lesion is actually still present, a default measurement of 0.5 cm should be applied. If the radiologist believes the lesion has gone, a default measurement of 0.0cm should be recorded.

## 10.2 Objective Status at Each Disease Evaluation

Objective Status is to be recorded at each evaluation. All measurable lesions up to a maximum of 2 lesions per organ 5 lesions in total, representative of all involved organs, should be identified as *target* lesions at baseline. All other lesions (or sites of disease) including any measurable lesions over and above the 5 target lesions should be identified as *non-target* lesions. Measurements must be provided for target measurable lesions, while presence or absence must be noted for non-target measurable and non-measurable disease.

For studies that use disease progression as an endpoint, whole body scanning at specific intervals is necessary to determine that progression is NOT present outside of the “target” areas. Therefore, in these studies it is not acceptable to image only the “target” areas of the body in follow-up scans. For study-specific imaging requirements, see the Study Calendar in [Section 9.0](#).

- a. **Complete Response (CR):** Complete disappearance of all target and non-target lesions (with the exception of lymph nodes mentioned below). No new lesions. No disease related symptoms. Any lymph nodes (whether target or non-target) must have reduction in short axis to < 1.0 cm. All disease must be assessed using the same technique as baseline.
- b. **Partial Response (PR):** Applies only to patients with at least one measurable lesion. Greater than or equal to 30% decrease under baseline of the sum of appropriate diameters of all target measurable lesions. No unequivocal progression of non-measurable disease. No new lesions. All target measurable lesions must be assessed using the same techniques as baseline.
- c. **Stable:** Does not qualify for CR, PR, Progression or Symptomatic Deterioration. All target measurable lesions must be assessed using the same techniques as baseline.
- d. **Progression:** One or more of the following must occur: 20% increase in the sum of appropriate diameters of target measurable lesions over smallest sum observed (over baseline if no decrease during therapy) using the same techniques as baseline, as well as an absolute increase of at least 0.5 cm. Unequivocal progression of non-measurable disease in the opinion of the treating physician (an explanation must be provided). Appearance of any new lesion/site. Death due to disease without prior documentation of progression and without symptomatic deterioration (see [Section 10.2e](#)).

Notes regarding new lesions: FDG-PET imaging can complement regular scans in identifying new lesions according to the following algorithm.

1. Negative FDG-PET at baseline, with a positive FDG-PET at follow-up is a sign of progression based on a new lesion.
2. No FDG-PET at baseline and a positive FDG-PET at follow-up corresponding to a potential new site of disease must have a confirmation by anatomical assessment (e.g. CT, MRI, x-ray) as new site of disease to be considered progressive disease. In such a case, the date of progressive disease will be the date of the initial abnormal FDG-PET.

- e. **Symptomatic deterioration:** Global deterioration of health status requiring discontinuation of treatment without objective evidence of progression. Efforts should be made to obtain objective evidence of progression after discontinuation.
- f. **Assessment inadequate, objective status unknown.** Progression or symptomatic deterioration has not been documented, and one or more target measurable lesions have not been assessed or inconsistent assessment methods were used.
- g. Objective status notes:
  - 1. Non-measurable and non-target measurable disease do not affect Objective Status in determination of CR (must be absent--a patient who otherwise has a CR, but who has non-measurable or non-target measurable disease present or not assessed, will be classified as having a PR). However, non-measurable and non-target lesions are included in determination of progression (if new sites of disease develop or if unequivocal progression occurs in the opinion of the treating physician).
  - 2. An objective status of PR or stable cannot follow one of CR. Stable can follow PR only in the rare case that tumor increases too little to qualify as progression, but enough that a previously documented 30% decrease no longer holds.
  - 3. In cases for which initial flare reaction is possible (hypercalcemia, increased bone pain, erythema of skin lesions), objective status is not progression unless either symptoms persist beyond 4 weeks or there is additional evidence of progression.
  - 4. Lesions that appear to increase in size due to presence of necrotic tissue will not be considered to have progressed.
  - 5. For bone disease documented on bone scan only, increased uptake does not constitute unequivocal progression. However, increase in the soft tissue component of a lesion as measured by CT or MRI would constitute progression.
  - 6. Appearance of new pleural effusions does not constitute unequivocal progression unless cytologically proven of neoplastic origin, since some effusions are a toxicity related to therapy or other medical conditions. Increase in the size of an existing effusion does not constitute unequivocal progression, since the fluid status of the patient could alter the size of the effusion.
  - 7. If CR determination depends on a lesion for which the status is unclear by the required tests, it is recommended the residual lesion be investigated with biopsy.

